The proposed project is a four parallel-condition, randomized controlled trial to assess the efficacy of the use of incentives and case management for increasing CR participation in a lower-SES cardiac population. The study population will be comprised of 209 lower-SES patients with a recent CR-qualifying coronary event (including congestive heart failure). The experimental conditions will be: 1) an intervention where patients are assigned a case manager (CM) to coordinate their care 2), an intervention wherein patients earn financial incentives (FI) contingent on participating in CR, or 3) a combination of these two interventions (FI+CM). These intervention conditions will be compared to a usual care control (i.e., referral to CR). The main outcome measure for this project will be CR participation and adherence (% who complete 30+ sessions, # of sessions completed). Secondary outcomes will include improvements in executive function, fitness (PVO2), and quality of life over four months and at one-year follow-up, as well as rehospitalizations and emergency department visits through one-year follow-up. A comprehensive cost effectiveness analysis of the interventions will be conducted, incorporating rehospitalization rates and the cost of both delivering and receiving the treatment.

Procedures: *Describe all procedures (sequentially) to which human participants will be subjected. Identify all procedures that are considered experimental and/or procedures performed exclusively for research purposes. Describe the types, frequency and duration of tests, study visits, interviews, questionnaires, etc. Include required screening procedures performed before enrollment and while on study. Please provide in table, list or outline format for ease of review. (describe and attach all instruments)*

Note: *A clinical research protocol may involve interventions that are strictly experimental or it may involve some aspect of research (e.g., randomization among standard treatments for collection and analysis of routine clinical data for research purposes). It is important for this section to distinguish between interventions that are experimental and/or carried out for research purposes versus those procedures that are considered standard therapy. In addition, routine procedures performed solely for research purposes (e.g., additional diagnostic/follow-up tests) should be identified.*

All procedures are being undertaken for research purposes.

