Power: Sample sizes were calculated to provide sufficient power to calculate differences in our primary outcome (CR adherence, as measured by % completing 30+ sessions) between the control condition and any of the three intervention conditions as well as between the combined intervention and either of the interventions delivered alone. Of most relevance, preliminary data from a previous trial on the use of incentives to increase CR rates among lower-SES individuals show that 54% of those receiving incentives completed the 30+ sessions compared to 28% of those receiving usual care. Using these proportions and the likelihood ratio test for two proportions in SAS POWER, 57 individuals per condition would be needed to detect a significant difference between conditions with 80% power. A seminal set of studies, conducted by Co-I [name], that systematically determined the efficacy of case management and incentives, alone and in combination, on cocaine abstinence, provided additional data for the power estimates.⁵⁴⁻⁵⁸ Using effect sizes from these five studies, the maximum estimated number of participants needed per condition is 50 to detect a significant difference in treatment adherence in combined intervention vs. single intervention with 80% power. Comparing any of the interventions singly or combined to usual care at four months post-treatment is estimated to require at most 25 participants per condition. Supporting these estimates, additional studies on the use of case management or incentives for adherence to other health-related behaviors have demonstrated effect sizes comparable to the studies referenced above.^{66,67,73,106,107} As such, the proposed sample size of 209 randomized subjects (57/intervention condition, 38 control) will allow us to conduct all pre-planned pairwise comparisons of the primary outcome measure (program adherence) with 80% power.

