Data Analysis: Treatment conditions will be compared for differences in baseline demographic characteristics using one-way Analysis of Variance (ANOVA) (or a nonparametric alternative, such as the Kruskal-Wallis Test) for continuous measures and chi-square tests (or Fisher's Exact Test) for categorical variables. If specific characteristics differ significantly across treatment conditions and are predictive of treatment outcomes, they will be considered as covariates in subsequent analyses. Primary analyses will include all subjects randomized to treatment conditions independent of early dropout or non-adherence, consistent with an intent-to-treat approach for randomized clinical trials.¹⁴⁷

The primary outcome measure in this trial will be CR adherence (% completing 30+ sessions) compared between the control condition and any of the three intervention conditions as well as between the combined intervention and either of the interventions delivered alone. Proportions completing all CR sessions will be examined across conditions using the test for differences between two population proportions (z), with 95% confidence intervals on effect sizes. To look at other measures of attendance, Cox proportional hazard models will be used to test differences in number of CR sessions completed

(i.e., time to dropout) between conditions. Purposeful selection of covariates will be used to build models.¹⁶⁴ Once final models have been derived, we will generate estimated hazard ratios with 95% confidence intervals and graphs of covariate-adjusted survival functions. Across all tests, statistical significance will be defined as $p < 0.05$ (2-tailed).

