Note: Only those individuals authorized to solicit consent may sign the consent form confirming that the prospective subject was provided the necessary information and that any questions asked were answered.

Patients who are hospitalized, or being cared for, due to a recent cardiac event and are enrolled in Medicaid, or have less than a high school education will be approached for possible inclusion by the PI or a trained representative. Patients will be given an unlimited amount of time to decide about participating in the study. A consent form with appropriate HIPAA language will be used for this study. Patients will have the option of electronic consent or consenting in person. UVM Staff will email a unique link to a redcap survey. We will go through the consent form verbally over the phone and the patient will have an opportunity to ask any questions they may have prior to consenting to be in the study.

Information Withheld From Subjects: Will any information about the research purpose be withheld from potential or participating subjects? If so, explain and justify the non-disclosure and describe plans for post-study debriefing.

Not applicable

Statistical Analysis Plan

Sample Size and Power

Sample sizes were calculated to provide sufficient power to calculate differences in our primary outcome (CR adherence, as measured by % completing 36 sessions) between the control condition and any of the three intervention conditions as well as between the combined intervention and either of the interventions delivered alone. Estimates were based on a series of studies conducted within our research group.

Of most relevance, preliminary data from our prior trial on the use of incentives to increase CR rates among lower-SES individuals showed 54% of those receiving incentives completed the 36 sessions compared to 28% of those receiving usual care. Using these proportions and the likelihood ratio test for two proportions in SAS POWER, 56 individuals per condition would be needed to detect a significant difference between conditions with 80% power.

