The primary outcome measure in this trial will be CR adherence (% completing 36 sessions) compared between the control condition and any of the three intervention conditions as well as between the combined intervention and either of the interventions delivered alone. Proportions completing all CR sessions will be examined across conditions using the test for differences between two population proportions (z), with 95% confidence intervals on effect sizes. Cox proportional hazard models will be used to test differences in number of CR sessions completed (i.e., time to dropout) between conditions. Purposeful selection of covariates will be used to build models.¹⁶⁴ These covariates will include baseline characteristics in addition to demographics, such as maximal exercise capacity, EF, socio-cognitive status, and quality of life. Variables that discriminate between participants by condition at a p-value of 0.25 or less using univariable tests will be included in an initial multivariable model. Once a reduced model is determined, discarded variables will be tested as potential confounders one at a time. The linearity of continuous variables remaining in the reduced model will be tested using the fractional polynomial (fp) procedure in STATA 14.2. The best set of power terms modeling each continuous variable will be used for building a final model. Interactions between variables will also be tested in the final model, initially one at a time and then including all significant interactions from initial testing. Once a final model has been derived, the adequacy of the model will be evaluated by using residual analysis to test the proportional hazards assumption, subject-specific diagnostics to measure influence on model fit, and overall goodness-of-fit. We will generate estimated hazard ratios with 95% confidence intervals and graphs of covariate-adjusted survival functions.

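### The primary outcome is completion of 30 or more sessions in the protocol but of 36 sessions in the SAP, with the same 54% and 28% planning rates given for both

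*Combined protocol and SAP*

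**What the plan says.** The protocol uses the lower threshold.

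- **Study Design:** "The main outcome measure for this project will be CR participation and adherence (% who complete 30+ sessions, # of sessions completed".
- **Statistical Considerations, Data Analysis:** "The primary outcome measure in this trial will be CR adherence (% completing 30+ sessions". The sentence that describes the test then reads: "Proportions completing all CR sessions will be examined across conditions". The programme is 36 visits (Financial Incentive Intervention), so this sentence implies 36, not 30.
- **Statistical Considerations, Power:** "54% of those receiving incentives completed the 30+ sessions compared to 28% of those receiving usual care", leading to "57 individuals per condition would be needed to detect a significant difference between conditions with 80% power".

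The SAP uses the full programme.

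- **Sample Size and Power:** "CR adherence, as measured by % completing 36 sessions", with planning rates "54% of those receiving incentives completed the 36 sessions compared to 28% of those receiving usual care". The resulting requirement is 56 per condition.
- **Primary and Secondary Data Analyses:** "The primary outcome measure in this trial will be CR adherence (% completing 36 sessions". The test sentence about all sessions is repeated here.

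Both documents plan a two-proportion z test, two-sided at 0.05, for the same five comparisons: each intervention against control, and the combination against each single intervention. Both settle on 57 per intervention arm and 38 controls.

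**The concern.** The rule that decides who counts as a success differs between two parts of the current text, and nothing says which part governs or that the outcome was changed. Anyone who completes 30 to 35 sessions is classified differently under the two definitions, in all five comparisons. The choice could therefore be made after the data are seen, and either choice could be presented as pre-specified.

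The planning rates are also tied to no single threshold. If 54% and 28% describe 30 or more sessions, the 36-session rates are probably lower. If they describe 36 sessions, the 30-session rates are probably higher. The power at the threshold eventually used is then not the power that was calculated.

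**Working it through.** **1. Reproduce the planned sample size.** Inputs from both power sections: p₁ = 0.54, p₂ = 0.28, likelihood ratio test, 80% power. Two-sided α = 0.05 comes from the analysis sections. With p̄ the weighted mean rate, the noncentrality is

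λ = 2 Σ nᵢ [pᵢ ln(pᵢ/p̄) + (1 − pᵢ) ln((1 − pᵢ)/(1 − p̄))],

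and power is the probability that a noncentral chi-square (1 df, λ) exceeds 3.84.

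| n per arm (equal arms) | Power |
|---|---|
| 55 | 79.7% |
| 56 | 80.4% |
| 57 | 81.1% |

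The smallest adequate n is 56, and 57 also suffices. The arithmetic is sound. It depends only on the two rates, so it cannot show which threshold they belong to.

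**2. Can the rates fit both thresholds?** Every 36-session completer is also a 30-session completer. The two rates within an arm are equal only if, apart from rounding, nobody stopped at 30 to 35. The documents do not say this.

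**3. Effect on the result.** Take counts near the planning rates: 0.54 × 57 = 30.8, so 31/57; 0.28 × 38 = 10.6, so 11/38. The test is z = (p̂₁ − p̂₂) / √[p̄(1 − p̄)(1/57 + 1/38)]. For 31/57 and 11/38, p̄ = 42/95 = 0.442 and z = 0.2544/0.1040 = 2.45.

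| Scenario | Incentives | Control | z | p |
|---|---|---|---|---|
| Base | 31/57 | 11/38 | 2.45 | 0.0145 |
| Base is 30+; 3 incentive participants stopped at 30–35 | 28/57 | 11/38 | 1.96 | 0.0502 |
| Base is 30+; 4 incentive participants stopped at 30–35 | 27/57 | 11/38 | 1.80 | 0.073 |
| Base is 30+; 3 incentive, 1 control stopped at 30–35 | 28/57 | 10/38 | 2.22 | 0.026 |
| Base is 36; 2 controls reached 30–35 | 31/57 | 13/38 | 1.93 | 0.053 |
| Base is 36; 3 controls reached 30–35 | 31/57 | 14/38 | 1.68 | 0.093 |
| Base is 36; 3 incentive, 2 control reached 30–35 | 34/57 | 13/38 | 2.43 | 0.015 |

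A one-sided shift of two to four people moves the result across 0.05. A balanced shift does not.

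**4. Effect on power.** Likelihood ratio test at the actual 57 versus 38. The base is 71.7%; its shortfall from 80% comes from the smaller control arm and is a separate matter. Only differences from 71.7% bear on this point.

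| Assumption | Rates at the other threshold | Power |
|---|---|---|
| 54/28 are 30+; 90% of completers reach 36 | 48.6% v 25.2% | 64% |
| 54/28 are 30+; 75% reach 36 | 40.5% v 21.0% | 52% |
| 54/28 are 30+; 50% reach 36 | 27.0% v 14.0% | 34% |
| 54/28 are 30+; both arms lose 5 points | 49% v 23% | 74% |
| 54/28 are 30+; both arms lose 10 points | 44% v 18% | 77% |
| 54/28 are 36; 10% of non-completers reach 30–35 | 58.6% v 35.2% | 61% |
| 54/28 are 36; 20% of non-completers reach 30–35 | 63.2% v 42.4% | 52% |
| 54/28 are 36; both arms gain 5, 10 or 15 points | 59 v 33, 64 v 38, 69 v 43 | 71%, 71%, 71% |

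The documents supply none of these fractions.

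**5. Could the band be occupied?** During contact restrictions the protocol expects two remote sessions a week. Four months is about 17.3 weeks (4 × 52/12), or about 35 sessions. If counting stopped at four months, a fully adherent remote participant would meet 30 but not 36. No section says that counting stops then.

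**The case against.** The contradiction itself cannot be read away, but several points limit what follows from it.

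- **56 versus 57 per condition is immaterial.** Both exceed 80% with equal arms, and the SAP also concludes with 57 per intervention arm and 38 controls. This stands; the difference shows only that the two texts were not kept aligned.
- **The changes in significance are possible, not shown to be likely.** The 0.0502 case sits on the boundary, and nothing in the documents supports a figure such as half of completers stopping short. Balanced shifts leave the conclusion unchanged, and equal absolute changes leave power about the same or raise it. This stands, and the tables include those cases.
- **A time frame exists.** Visits are scheduled over four months, and end of treatment is set at four months. That is a schedule, not a rule for when a session stops counting towards the primary outcome, and the SAP times its survival analysis to completion or dropout. The gap is therefore narrow, and it applies at either threshold.
- **Number of sessions is analysed by a Cox model in both documents.** Some attendance results therefore do not depend on the cut-off. This does not settle the binary primary outcome.

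**Conclusion.** The concern holds. Two definitions of the primary outcome stand in the current text, the protocol's Data Analysis section mixes both, and the same planning rates are assigned to each. This is a contradiction in the variable on which the trial's conclusion rests, and it must be resolved before outcome data are analysed.

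The contradiction rests on the text alone. Its numerical effect depends on how many people stop at 30 to 35 sessions and in which arms, which the documents do not give. Under the assumptions shown, p ranges from 0.015 to 0.093 and power from 34% to 77%, against 0.0145 and 71.7% at the base.

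**What to change.** Before outcome data are analysed, the sponsor should:

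1. Confirm one threshold and state it in the protocol (Study Design; Power; Data Analysis) and the SAP (Sample Size and Power; Primary and Secondary Data Analyses). Thirty or more is a reasonable candidate, since the protocol names it wherever it defines the outcome. The 36-visit programme and the test sentence point the other way, and the documents do not show which was intended.
2. Reword the sentence on proportions completing all sessions, in both documents, to match.
3. Give the prior-trial rates observed at the chosen threshold. If they differ from 54% and 28%, restate the per-condition n and the power at 57 versus 38.
4. Report the other threshold as a named sensitivity analysis.
5. State the period over which sessions count towards the primary outcome. This matters most if 36 is kept.

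The cost is a wording change in both documents and a look-up in the research group's own prior trial. No change to conduct or data collection is needed.

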Study Measures: Study measures are taken by clinical staff blinded to treatment condition at three timepoints: baseline, end of treatment (four months) and one-year follow-up.

Demographic Information: We will collect the following sociodemographic data: age, gender, educational attainment, race/ethnicity, smoking status, marital status, and health insurance status at baseline. These demographic measures will allow us to characterize the population.

CO level: Carbon Monoxide level (CO) will be collected using a coVita carbon monoxide measuring device. The participant will be required to breathe slowly through a cardboard tube to obtain this measurement. This measurement will quantify recent exposure to carbon monoxide (e.g. smoke/secondhand smoke/car exhaust/heater emissions).

Maximal Exercise Capacity: Maximal exercise capacity will be assessed on a treadmill using measurements of peak oxygen uptake, duration of treadmill exercise and maximal exercise intensity in METS. A continuous modified-Balke protocol will be used, with exercise increasing gradually at 1 MET increments at 2-minute intervals. Exercise is EKG monitored and stopped prior to exhaustion if the patient develops progressive angina, > 2mm ST segment depression, exercise induced hypertension (230 systolic, 105 diastolic), severe arrhythmias, dizziness or symptomatic hypotension. The occurrence of any concerning responses, other than high threshold angina, excludes a patient from the training protocol unless effective therapy is instituted. Patients will perform the maximal stress test taking their usual medications at a standardized time of day. The clinical staff at UVMMC have extensive experience

measuring peak exercise capacity in patients in the CR setting.¹²⁷ In lieu of a maximal stress test at CR exit, estimated METS while exercising on the treadmill may be used at the final CR session as a clinical measure of fitness at exit.

Socio-Cognitive Measures: We will assess current depressive symptoms (Beck Depression Inventory, BDI, Patient Health Questionnaire (PHQ-2)^{128,129} as well self-reported adaptive functioning and problems (ASEBA - Achenbach System of Empirically Based Assessment.¹³⁰ We will also assess self-reported social support (ISEL - Interpersonal support evaluation list).¹⁴⁷

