Whenever possible, paper questionnaires will be completed remotely, either by mail (completed and returned by the study participant) or with the researcher over the phone. If in-person research visits are not allowed the following assessments will not be collected: IQ test (WASI), Stop Signal Task (SST), Delay Discounting Task (DD), Trail Making Task (TMT), Digit Span Task. If in-person research visits are allowable these assessments will be completed using appropriate distancing measures and PPE as is outlined in our approved lab safety reopening plan (attached).

Statistical Considerations: *Delineate the precise outcomes to be measured and analyzed. Describe how these results will be measured and statistically analyzed. Delineate methods used to estimate the required number of subjects. Describe power calculations if the study involves comparisons. Perform this analysis on each of the primary and secondary objectives, if possible.*

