By definition, primary outcome data will not be missing since it focuses on program participation. For other variables, minor amounts of missing data, due to factors other than dropout from the CR program, will be ignored, leading to deletion of cases in regression analyses. However, if substantial amounts of missing data of key predictor variables exist, we will explore the randomness of missing data using Little's MCAR (missing completely at random) test in SPSS 24. If we cannot reject the null hypothesis, we will proceed to use multiple imputation procedures in SAS 9.4 (PROC MI and PROC MIANALYZE) to generate results based on imputed data.

Although this study is powered for our primary outcome of adherence to CR, we will also carefully examine improvements in fitness, and other health outcomes (quality of life, maximal exercise capacity, weight, waist measurements) between conditions, using the pre-planned comparisons outlined for the primary outcome. Additionally, we will examine changes in executive function measures and socio-cognitive status at 4 and 12 months. Changes in these scores will also be examined for possible gender interactions. Since multiple observations for each participant will be obtained, the general analytic approach will consist of analysis of covariance (ANCOVA) at 4 months and repeated measures analysis of variance (ANOVA) at 12 months. Formal testing will examine the condition by time interaction term to assess differential time changes between treatment conditions. Post-hoc comparisons between conditions will be made if significant interactions are observed.

Survival analyses will be conducted once all participants have completed the 36 sessions of their CR program (or, alternatively, have dropped out of the program). Preliminary analyses of all other outcome measures will occur upon collection of all 4-month measures across all participants. Final analyses of secondary outcome measures, using repeated measures procedures, will be conducted upon collection of all 12- month measures across all participants. Across all tests, statistical significance will be defined as $p < 0.05$ (2-tailed).

Cost Effectiveness Analyses

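### Covariate imputation depends on failing to reject MCAR, with no method if it is rejected, and secondary outcomes missing after CR dropout have no stated rule

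*Combined protocol and SAP*

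**What the plan says.** The SAP (Primary and Secondary Data Analyses) takes the primary outcome to be always observed. For all other variables it gives two rules.

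- Minor gaps: "minor amounts of missing data, due to factors other than dropout from the CR program, will be ignored, leading to deletion of cases".
- Substantial gaps: "if substantial amounts of missing data of key predictor variables exist, we will explore the randomness of missing data using Little's MCAR", followed by "If we cannot reject the null hypothesis, we will proceed to use multiple imputation procedures in SAS 9.4 (PROC MI and PROC MIANALYZE".

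Nothing is said about what happens if the test rejects.

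The predictors concerned are mainly the candidate covariates of the Cox models: "These covariates will include baseline characteristics in addition to demographics, such as maximal exercise capacity, EF, socio-cognitive status, and quality of life". The protocol (Data Analysis) sets those models apart from the primary comparison: "To look at other measures of attendance, Cox proportional hazard models will be used to test differences in number of CR sessions completed".

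For the secondary outcomes, "the general analytic approach will consist of analysis of covariance (ANCOVA) at 4 months and repeated measures analysis of variance (ANOVA) at 12 months". Neither the SAP nor the protocol adds a rule for missing outcome values or says how the repeated-measures model is fitted. The intent-to-treat sentence, which appears in both, is limited to the primary analyses.

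**The concern.** The null hypothesis of Little's test is MCAR. The plan therefore offers imputation when the data look compatible with MCAR and is silent when the test finds that missingness is related to observed data. The silent branch is where a MAR-based method has most to offer.

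The second gap is separate. The deletion rule excludes missingness caused by CR dropout, and the imputation rule covers predictors. An outcome missing at 4 or 12 months because the participant left CR falls between the two. The planning rates in the SAP (54% completing with incentives, 28% with usual care) imply that 46% and 72% do not complete, so the excluded group is large. Secondary objective 1, whether attendance differences affect health and quality of life, rests on these outcomes. With no rule in place, the handling may be settled after the data are seen.

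**Working it through.** The plan has no missing-data figure to reproduce. The only document inputs are the completion rates, 54% and 28%, and N = 209. All missingness rates below are assumptions.

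**1. The gate.** Four facts show that the test cannot choose the method.
- Imputation is valid under MCAR, where it mainly adds precision.
- It is also valid under MAR, where it is most useful.
- Failing to reject does not establish MCAR.
- Rejecting does not separate MAR from MNAR.

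**2. How the gate behaves.** This was simulated with 209 participants, complete age and smoking, one covariate 20% missing overall, 4000 replicates and a 0.05 level.

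| Missing, <57 / ≥57 years | Little's test rejects (no method stated) |
|---|---|
| 20 / 20% | about 5% |
| 15 / 25% | 23% |
| 10 / 30% | 75% |
| 5 / 35% | 99% |

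At 15/25% the age dependence goes undetected in 77% of trials. At 5/35% the plan almost always has no method. These are frequencies and say nothing about bias.

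**3. Cost for covariates.** The plan does not say that cases are deleted on rejection. If they were, losing 20% of cases would inflate a standard error by about 1/√0.8 = 1.12. Four covariates each 10% missing independently would leave 0.9⁴ = 0.656 of cases (137 of 209), a factor of 1/√0.656 = 1.23. A Cox simulation that included age and pooled the intervention arms (171 vs 38) gave standard deviations about 11% and 21% larger with deletion than with imputation, and no visible bias. It is not the planned pairwise model, so it is illustrative only.

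**4. Coverage for outcomes.** The nearest other provisions do not fill the gap.
- The estimated-METS substitute (protocol, Study Measures) needs a final CR session.
- The contact-restriction text lists what will not be collected: "If in-person research visits are not allowed the following assessments will not be collected: IQ test (WASI), Stop Signal Task (SST" and other in-person tasks. It gives no analysis rule.
- ANCOVA uses only participants with a 4-month value. Classical repeated measures ANOVA uses only those with every visit.

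**5. Size for outcomes.** Suppose that only completers gain, by one unit. The true contrast is then 0.54 − 0.28 = 0.26. Let 10% of completers and a fraction m of non-completers be missing. The observed mean in an arm with completion rate p is

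p(0.90) / [p(0.90) + (1 − p)(1 − m)].

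For incentives at m = 0.20: 0.486 / (0.486 + 0.46 × 0.80) = 0.569. For usual care at m = 0.40: 0.252 / (0.252 + 0.72 × 0.60) = 0.368. The difference is 0.201.

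| Non-completers missing, incentives / usual care | Complete-case contrast | Change from 0.26 |
|---|---|---|
| 20 / 20% | 0.265 | +2% |
| 40 / 40% | 0.269 | +4% |
| 60 / 60% | 0.259 | −1% |
| 70 / 70% | 0.240 | −8% |
| 80 / 80% | 0.204 | −21% |
| 90 / 90% | 0.136 | −48% |
| 20 / 40% | 0.201 | −23% |
| 30 / 50% | 0.190 | −27% |
| 40 / 20% | 0.333 | +28% |

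With equal retention the contrast barely moves until about 70% of non-completers are missing. With unequal retention it moves at moderate rates, in either direction.

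**6. What attendance adds.** In this set-up, missingness is unrelated to gain once completion is known. Attendance is recorded for everyone. Weighting the observed completer and non-completer means by the full randomised shares returns 0.54 × 1 + 0.46 × 0 = 0.54 and 0.28 × 1 + 0.72 × 0 = 0.28, a difference of 0.26. This follows from the assumed mechanism, but it shows why sessions attended belongs in the imputation model.

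**The case against.** Leaving CR is not the same as missing an assessment. Assessments are fixed "at three timepoints: baseline, end of treatment (four months) and one-year follow-up", usual-care participants are expected at them, and each is paid, with travel reimbursed. Paper questionnaires are to be completed by mail or phone where possible under contact restrictions, which protects much of the quality-of-life and self-report data. This stands as a reason to expect moderate rather than extreme missingness. It does not make retention equal: case-managed participants have a contact available by phone six days a week, and usual care has none. In-person tasks still have no remote route.

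ANCOVA with no imputation has an ordinary default, the participants with observed values, and the SAP's wording on repeated-measures procedures does not exclude a likelihood-based fit. That is fair, but neither choice is written down.

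A reader might infer that the gate simply runs the wrong way, so that imputing after non-rejection is an error. It is not: imputation is valid under MCAR, and reversing the gate would be no better. A reader might also infer that contact-restriction gaps would trigger rejection. Those gaps would follow calendar period and may well pass the test. They show that gaps are likely, not that imputation would be withheld.

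**Conclusion.** Both gaps are real on the text. The gate is uninformative as a switch and has an empty branch, and outcomes missing after CR dropout have no rule. The effect is confined to the covariate-adjusted Cox models and the secondary outcomes. The documents do not support a claim that the primary result is compromised, because the unadjusted comparison of completion proportions uses neither rule.

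Nor do they support a claim of demonstrated bias. For covariates the likely cost is precision, and only if a selected covariate is substantially missing and cases are deleted. For outcomes, the complete-case contrast is nearly unbiased at 20-60% non-completer missingness if it is equal in both arms. It is attenuated by 8-48% at 70-90%, and shifted by roughly a quarter either way when retention differs between arms by 20 percentage points. These sizes rest on assumed missingness rates and on gain occurring in completers only. The point should be corrected before the data are analysed.

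**What to change.** Delete the Little's-test condition. State that substantially missing covariates are multiply imputed under MAR whatever any test shows.

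For the 4- and 12-month secondary outcomes, prespecify one of two methods, including all randomised participants:
- multiple imputation with condition, baseline value, the age and smoking strata, and sessions attended as an auxiliary variable; or
- a likelihood-based repeated-measures model that uses the same information.

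State which randomised participants enter each secondary analysis. The protocol's statement under Withdrawal Procedures that data from withdrawn participants are not kept is a separate matter, but it must be reconciled with that population.

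The cost is SAP wording and modest programming. PROC MI is already planned, and sessions attended are already collected.
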